Patient with pediatric sarcoma who have limited metastases are still potentially curable with aggressive local therapy. However, conventional moderate dose radiation is unlikely to provide durable local control. Given the recent technologic advances in radiation delivery, it is now possible to deliver tumoricidal doses, using stereotactic body radiotherapy (SBRT) over a short time course with highly focal techniques. Stereotactic radiation has proven efficacious in the intracranial setting and in multiple extracranial sites in adults. It has not yet been well studied in the pediatrics population where there is a particularly strong rationale due to the ablative doses that can be delivered to tumor while simultaneously reducing high dose to normal tissues. The proposed trial is a single arm phase II study to determine the efficacy of SBRT in pediatric sarcomas with surgically unresectable metastatic disease. Metastatic sites eligible for treatment in this study include bony sites of disease. SBRT will be delivered to each eligible site to a total dose of 4000 cGy delivered in 5 fractions of 800 cGy per fractions each day. Following completion of SBRT, patients will undergo treatment response assessment with the use of diagnostic imaging, clinical examination, and completion of the Brief Pain Inventory to assess quality of life. The primary objective of this study is to determine the efficacy of SBRT delivered to a dose of 4000 cGy in 5 fractions of 800 cGy each for patients greater than 3 years of age and \leq 40 years of age with metastatic disease of bone secondary to pediatric sarcoma. The secondary objectives of this study include describing the toxicity of SBRT with this regimen; assessing clinical response rate of each target lesion; assessing long-term clinical outcomes; and assessing quality of life following completion of treatment. For patients with potentially curable oligometastatic disease, surgical resection in conjunction with systemic therapy remains the standard of care. Patients on this study will be able to receive chemotherapy 2 weeks after completion of SBRT. Issues that may limit participation include our inability to assess late effects that may not develop till at least 10 years after therapy. For this reason, we will limit the population in this study to patients who are surgically unresectable and would be otherwise incurable with current standard systemic therapies.

SCHEMA

1. OBJECTIVES

1.1 Primary Objectives

To determine the lesion-specific local control at 6 months of SBRT delivered to a dose of 4000 cGy in 5 fractions of 800 cGy each for patients greater than 3 years of age and ≤ 40 years of age with metastatic disease of bone secondary to pediatric non-rhabdomyosarcoma soft tissue or bone sarcoma.

1.2 Secondary Objectives

1.2.1 To describe the toxicity of SBRT delivered to a dose of 4000 cGy in 5 fractions of 800 cGy each for the population enrolled using grading with CTCAE v. 4.0

1.2.2 To assess clinical response rate of each treated site by serial CT assessment (FDG- PET/CT is optional for assessment)

1.2.3 To assess long-term clinical outcomes of this patient population after completion of SBRT by measuring relapse-free survival and overall survival

1.2.4 To assess quality of life following completion of SBRT using pre- and post-SBRT completion of the Brief Pain Inventory form and 10 point Visual Analog scale which will be filled out by the patient

2. BACKGROUND

2.1 Oligometastatic Disease

Cancer is the second leading cause of death in the United States, primarily due to an inability to control metastatic disease. The metastatic capacity of cancers behaves along a spectrum of disease progression, such that some tumors have spread widely before clinical detectability and others never metastasize. Contained within this spectrum, is an oligometastatic state where metastases are limited in number and location. The presence of an oligometastatic state was originally proposed by Hellman who suggested that these oligometastatic patients would benefit from effective local therapy in addition to systemic therapy (1). In agreement with this hypothesis, surgery and chemotherapy for isolated pulmonary metastases can result in long term disease-free periods (2). Additionally, some 25% of patients following resection and chemotherapy for colorectal cancer and isolated liver metastases can similarly have longterm disease free survival (3-5). Patients who may benefit most from curative therapy are most likely those patients with limited systemic disease when metastatic disease is generally confined to a lesion state of five metastatic sites or fewer.

2.2 Stereotactic Body Radiotherapy (SBRT)

The treatment of metastases depends on multiple factors including 1) the location of the primary tumor, 2) the presence or absence of other metastatic foci, 3) the size, number and location of metastases, 4) the effectiveness of various forms of therapy, and 5) the patient's functional status. Conventional moderate dose radiation for metastatic disease is given primarily for palliation. Recent advances in radiation delivery now make it possible to image and treat precisely within any anatomical region of the body. As a result, the capacity to deliver tumoricidal doses in a single or few (1-10) outpatient treatments is now possible. In addition, by minimizing the irradiation of surrounding healthy tissue, it should also be possible to decrease the rate of complications. Intracranial stereotactic radiation therapy has been shown to be a highly effective treatment for brain metastases in both the adult and pediatrics population (6,7). This suggests that selective small extracranial tumors may be effectively controlled by similar focal high-dose stereotactic body radiotherapy (SBRT). Local control in excess of 75% has been reported using extracranial SBRT for metastatic tumors of the spine, lung and liver, which is significantly higher than conventional moderate dose radiation (8-24). Toxicity has been minimal in these reports despite the use of very high biological equivalent doses (8-24).

2.3 Rationale

The SBRT literature focuses on clinical outcomes in the adult population. However, SBRT has a particularly strong rationale for application in pediatrics given that high biologically effective doses have been shown to increase control in histologies, such as sarcoma, which are common in the pediatrics population (11,25). With stereotactic radiation therapy techniques, a reduction in normal tissue dose surrounding the target lesion of interest may also be accomplished resulting in lower toxicity. Given that pediatric patients with sarcomas, presenting with limited metastases in lung and bone, are still considered to be a curable

population with aggressive local therapy, SBRT could have a significant impact on outcomes in oligometastatic patients who may be otherwise unresectable (25-28).

3. PATIENT SELECTION

3.1 Inclusion Criteria

- 3.1.1 Patients must have histologically or cytologically confirmed nonrhabdomyosarcoma of soft tissue or bone at any site
- 3.1.2 Patients must have measurable disease, defined as at least one lesion that can be accurately measured in at least one dimension (longest diameter to be recorded) as ≥ 20 mm with conventional techniques or as ≥ 10 mm with spiral CT scan within 4 weeks of treatment start. See Section 9.1.3 for the evaluation of measurable disease.
- 3.1.3 Greatest tumor dimension of all sites must be ≤ 5.0 cm or <250 cm^3
- 3.1.4 There is at least 1 metastatic site at one or more of the following sites: spine or non-spine bone and at maximum 5 sites can be treated on protocol
- 3.1.5 Surgically unresectable site as determined by tumor board or surgeon or patients who decline surgery.
- 3.1.6 Patients must be greater than 3 years of age and ≤ 40 years of age.
- 3.1.7 Life expectancy of at least 9 months
- 3.1.8 Lansky performance status ≥ 50 (See Appendix E)
- 3.1.9 Ability to understand and the willingness to sign a written informed consent document and if a minor, have a guardian who meets the above criteria.

3.2 Exclusion Criteria

- 3.2.1 Patients who have had chemotherapy or radiotherapy within 2 weeks prior to starting radiation treatment
- 3.2.2 Patients who have had any prior radiotherapy to the treatment site(s).

- 3.2.4 A patient may not participate in a concurrent treatment protocol. All patients will be eligible to receive chemotherapy alone, systemic therapeutic agents, or conventional chemo-radiotherapy at the time of clinical or radiographic disease progression or at 2 weeks following completion of SBRT.
- 3.2.5 Pregnant women are excluded from this study because radiation treatment has known potential for teratogenic or abortifacient effects.
- 3.2.6 Refusal to take a pregnancy test prior to treatment if the patient is a woman with child bearing potential.
- 3.2.7 Patients with a rhabdomyosarcoma will be excluded due to the radiosensitive nature of their disease.

3.3 Inclusion of Women and Minorities

Both men and women and members of all races and ethnic groups are eligible for this trial.

4. REGISTRATION PROCEDURES

4.1 General Guidelines

Institutions will register eligible participants with the Coordinating Center. Registration must occur prior to the initiation of therapy.

A member of the study team will confirm eligibility criteria and complete the protocol-specific eligibility checklist.

Participants should begin protocol treatment within 3 weeks from simulation. Issues that would cause treatment delays should be discussed with the Principal Investigator. If a patient does not receive protocol therapy following registration, the Study Coordinator should be notified as soon as possible.

4.2 Registration Process

Prior to protocol enrollment and initiation of treatment, subjects must sign and date an IRB approved consent form. All patients must be registered centrally at the Johns Hopkins Sidney Kimmel Comprehensive Cancer Center.

To register a patient, the following documents should be completed and faxed or e-mailed to the Coordinating Center:

- Signed patient consent form
- HIPAA authorization form
- Completed and signed eligibility checklist
- De-identified copies of source documentation verifying eligibility

The Coordinating Center will review the documents to confirm eligibility. To complete the registration process, the Coordinating Center will:

- assign a patient study number
- register the patient on the study with the Sidney Kimmel Comprehensive Cancer Center's Clinical Research Office
- fax or e-mail the patient study number to the participating site

5. TREATMENT PLAN

Treatment will be administered on an outpatient basis. Expected toxicities and potential risks are described in Section 7. Appropriate dose modifications are described in Section 6. No investigational or commercial agents or therapies other than those described below may be administered with the intent to treat the patient's malignancy concurrently.

5.1 Pre-Treatment Procedures

The following will be completed prior to radiation initiation:

- Medical history and clinical examination
- Pathologic confirmation of malignancy
- CBC, chemistry panel
- CT of treatment site (not required if MRI is obtained)
- MRI of treatment site, optional depending on site (required for spinal lesions)
- Positron Emission Tomography (FDG-PET) scan (optional)

5.2 Simulation

Stereotactic radiation requires meticulous definition of the target, normal tissue structures, and visualization for localization during treatment delivery. Prior to treatment, a simulation CT scan will be performed for tumor localization using rigid immobilization appropriate for stereotactic treatment. A separate FDG-PETCT or MRI is optional for diagnostic purposes and can be used for treatment planning with fusion -- this study would be done identically if the patient were having standard fractionated radiation. These studies can assist with delineation of the target and visualization for stereotactic treatment. While MRIs are optional for diagnostic evaluation and treatment planning of non-spine bony sites, they are required for patients who will be treated to the spine.

Patients will be positioned in a reproducible treatment position with an appropriate immobilization device custom-made for each patient and specific to treatment site. A variety of immobilization systems can be used on study such as stereotactic frames which surround the patient on three sides or large rigid pillows that reference to a stereotactic coordinate system.

CT simulation will be performed. The simulation study must include the target and all organs at risk for treatment planning. Simulation scan length should be 510 cm superior and inferior to the target. All organs at risk within the scan length should be contoured for dose-volume histogram analysis. For stereotactic treatment, tomographic slice thickness of 1-3 mm through the target is recommended.

Special consideration should be given to the analysis of internal organ motion if the target lesion is located in a site subject to motion such as the chest wall. Techniques to image moving targets such as active breath-hold techniques, accelerator gating with respiratory cycle, tumor tracking, 4D CT scan acquisition in conjunction with maximum intensity projection (MIP), will be considered acceptable maneuvers to account for organ motion. If the target cannot be visualized or localized on the planning imaging modality as a result of motion or metal artifact, stereotactic treatment should not be used.

The treating radiation oncologist will identify the location of the tumor. Gross tumor volume (GTV) delineation will be performed with a diagnostic radiologist on sequential axial computed tomography images. A radiosurgical treatment plan will be developed based on tumor geometry and location. Adjacent normal structures including but not limited to the heart, esophagus, aorta, spinal cord, kidneys, rectum, bowel, liver, and stomach within 5 cm of the GTV will be identified for the purpose of limiting incidental radiation to these structures (please see Appendix D for a list of normal tissue dose constraints to be used on protocol as well as constraints for high and low-dose spillage).

We plan to deliver 800 cGy at each fraction for five fractions every day for a total dose of 4000 cGy, over a treatment duration at a maximum of 2 weeks. For bony sites aside from spine, the GTV will be expanded uniformly to the PTV by 2 mm and treated to 4000 cGy to cover at least 90% of the defined target volume. For patients with spinal metastases undergoing treatment on protocol, the vertebral body will be contoured as a separate clinical target volume (CTV) encompassing the GTV. The CTV vertebral body will be expanded by 2 mm to create a PTV. The GTV will be treated to 4000 cGy and the PTV treated to 3000 cGy in 5 fractions..

The main criteria for dose prescription will be the achievement of the spinal cord dose constraint (see table below):

Normal Tissue	Volume	Volume Max (cGy)	Max Point Dose (cGy)	Endpoint (\geq Grade 3)
Spinal Cord	<0.25 cc <1.2 cc	1550cGy 1000cGy	2000cGy (400cGy /fx)	Myelitis

The spinal cord will be contoured as the true cord with use of MRI for fusion. Spinal cord volume will be defined as 6 mm above and below the radiosurgery target volume. The spinal cord can move within the thecal sac. The thecal sac will be contoured based on T2 MRI or bony limit of spinal canal and will serve as a PRV (planning organ at risk volume) for the spinal cord. Thecal sac volume will be defined as 6 mm above and below the radiosurgery target volume. The skin will be defined as the outer 0.5 cm of the body surface. The skin is essentially a rind of 0.5 cm enveloping the entire body in axial planes. The cranial and caudal surface of the superior and inferior limits of the planning CT should not be contoured as skin unless skin is actually present in these locations. Ribs within 5 cm of the PTV should be contoured by outlining bone and bone marrow. The intercostal spaces should not be included as part of the ribs. The minimum, mean, and maximum dose to the PTV will be reported. Only \leq 1 cc or \leq 1-5% of unspecified tissue outside of the PTV can receive \geq 100-110% of the prescribed dose.

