APPENDIX D DOSE CONSTRAINTS

Dose Constraints for Five Fractions – Based upon the AAPM Report TG 101³² reduced by 10% based on the assumption that patients on protocol have received prior systemic chemotherapy.

Serial Tissue	Volume	Volume Max (Gy)	Max Point Dose (Gy)	Endpoint (\geq Grade 3)
Optic Pathway	<0.2 cc	18 Gy (3.6 Gy/fx)	22.5 Gy (4.5 Gy/fx)	neuritis
Cochlea			24.7 Gy (4.95 Gy/fx)	hearing loss
Brainstem	<1 cc	23.4 Gy (4.68 Gy/fx)	31 Gy (6.2 Gy/fx)	cranial neuropathy
Spinal Cord	<0.25 cc	20.2 Gy (4.05 Gy/fx)	27 Gy (5.4 Gy/fx)	myelitis
	<1.2 cc	12.1 Gy (2.43 Gy/fx)		
Thecal Sac	<2.5 cc	20.2 Gy (4.05 Gy/fx)	30 Gy (6 Gy/fx)	myelitis
	<5 cc	15 Gy (3 Gy/fx)		
Cauda Equina	<5 cc	27 Gy (5.4 Gy/fx)	28.8 Gy (5.76 Gy/fx)	neuritis
Sacral Plexus	<3 cc	27 Gy (5.4 Gy/fx)	28.8 Gy (5.76 Gy/fx)	neuropathy
Rib	<1 cc	31.5 Gy (6.3 Gy/fx)	38.7 Gy (7.74 Gy/fx)	Pain or fracture
Esophagus*	<5 cc	24.7 Gy (4.95 Gy/fx)	31.5 Gy (6.3 Gy/fx)	stenosis/fistula
Ipsilateral Brachial Plexus	<3 cc	27 Gy (5.4 Gy/fx)	28.8 Gy (5.76 Gy/fx)	neuropathy
Heart/Pericardium	<15 cc	28.8 Gy (5.76 Gy/fx)	34.2 Gy (6.84 Gy/fx)	pericarditis
Great vessels	<10 cc	42.3 Gy (8.46 Gy/fx)	47.7 Gy (9.54 Gy/fx)	aneurysm
Trachea and Ipsilateral Bronchus*	<4 cc	16.2 Gy (3.24 Gy/fx)	34.2 Gy (6.84 Gy/fx)	stenosis/fistula
Skin	<10 cc	27 Gy (5.4 Gy/fx)	28.8 Gy (5.76 Gy/fx)	ulceration
Stomach	<10 cc	25.2 Gy (5.04 Gy/fx)	28.8 Gy (5.76 Gy/fx)	ulceration/fistula
Duodenum*	<5 cc	16.2 Gy (3.24 Gy/fx)	28.8 Gy (5.76 Gy/fx)	ulceration
Jejunum/Ileum*	<5 cc	17.5 Gy (3.51 Gy/fx)	31.5 Gy (6.3 Gy/fx)	enteritis/obstruction
Colon*	<20cc	22.5 Gy (4.5 Gy/fx)	34.2 Gy (6.84 Gy/fx)	colitis/fistula
Rectum*	<20cc	22.5 Gy (4.5 Gy/fx)	34.2 Gy (6.84 Gy/fx)	proctitis/fistula
Bladder wall	<15 cc	16.4 Gy (3.28 Gy/fx)	34.2 Gy (6.84 Gy/fx)	cystitis/fistula
Penile Bulb	<3 cc	27 Gy (5.4 Gy/fx)	45 Gy (9 Gy/fx)	impotence
Femoral Heads (Right & Left)	<10 cc	27 Gy (5.4 Gy/fx)		necrosis
Renal hilum/vascular trunk	<2/3 volume	20.7 Gy (4.14 Gy/fx)		malignant hypertension
Parallel Tissue	Volume	Critical Volume Dose		Endpoint (\geq Grade 3)
Lung (Right & Left)	1500 cc	11.2 Gy (2.25 Gy/fx)		Basic Lung Function
Lung (Right & Left)	1000 cc	12.1 Gy (2.4 Gy/fx)		Pneumonitis
Liver	700 cc	18.9 Gy (3.78 Gy/fx)		Basic Liver Function
Renal cortex (Right & Left)	200 cc	15.7 Gy (3.15 Gy/fx)		Basic renal function

*Avoid circumferential irradiation

Guidelines for Spillage

High Dose Spillage:

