1. Any dose > 105% of the prescription dose should occur primarily within the PTV itself and not within the normal tissues outside the PTV. Therefore, the cumulative volume of all tissue outside the PTV receiving a dose > 105% of prescription dose should not be more than 15% of the PTV volume.
2. Conformality of PTV coverage will be judged such that the ratio of the volume of the prescription isodose meeting criteria 1 through 4 to the volume of the PTV is ideally < 1.2 (see table below). These criteria will not be required to be met in treating very small tumors (< 2.5 cm axial GTV dimension or < 1.5 cm craniocaudal GTV dimension) in which the required minimum field size of 3.5 cm results in the inability to meet a conformality ratio of 1.2.

Low Dose Spillage

1. The falloff gradient beyond the PTV extending into normal tissue structures must be rapid in all directions and meet the following criteria:
 - a. The maximum total dose over all fractions in Gray (Gy) to any point 2 cm or greater away from the PTV in any direction must be no greater than D2cm where D2cm is given by the table below.
2. The ratio of the volume of 50% of the prescription dose isodose to the volume of the PTV must be no greater than R50% where R50% is given. See Table below.
3. Respect all critical organ dose-volume limits listed above

Table 1: Conformality of Prescribed Dose for Calculations Based on Deposition of Photon Beam Energy in Heterogeneous Tissue

PTV Volume (cc)	Ratio of Prescription Isodose Volume to the PTV volume		Ratio of 50% Prescription Isodose Volume to the PTV Volume, R50%		Maximum dose (in% of dose prescribed) @ 2 cm from PTV in Any Direction, D2cm (Gy)		Percent of Lung Receiving 20 Gy Total or More, V20 (%)	
1.8	<1.2	<1.5	<5.9	<7.5	<50.0	<57.0	<10	<15
3.8	<1.2	<1.5	<5.5	<6.5	<50.0	<57.0	<10	<15
7.4	<1.2	<1.5	<5.1	<6.0	<50.0	<58.0	<10	<15
13.2	<1.2	<1.5	<4.7	<5.8	<50.0	<58.0	<10	<15
22.0	<1.2	<1.5	<4.5	<5.5	<54.0	<63.0	<10	<15
34.0	<1.2	<1.5	<4.3	<5.3	<58.0	<68.0	<10	<15
50.0	<1.2	<1.5	<4.0	<5.0	<62.0	<77.0	<10	<15
70.0	<1.2	<1.5	<3.5	<4.8	<66.0	<86.0	<10	<15
95.0	<1.2	<1.5	<3.3	<4.4	<70.0	<89.0	<10	<15
126.0	<1.2	<1.5	<3.1	<4.0	<73.0	>91.0	<10	<15

163.0	<1.2	<1.5	<2.9	<3.7	<77.0	>94.0	<10	<15
-------	------	------	------	------	-------	-------	-----	-----

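### Appendix D lists looser spinal cord limits than Section 5.2 (27 Gy against 20 Gy maximum), and no sentence says that Section 5.2 overrides them

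*Combined protocol and SAP*

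**What the plan says.** Section 5.2 deals with the spinal cord twice.

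- It names the cord among the structures to be identified when they lie within 5 cm of the GTV, and directs the planner onward: "please see Appendix D for a list of normal tissue dose constraints to be used on protocol". Nothing limits this to spine or to non-spine targets.
- After the spine prescription (GTV 4000 cGy, PTV 3000 cGy, five fractions) it says: "The main criteria for dose prescription will be the achievement of the spinal cord dose constraint". The table that follows has one row, the spinal cord. The volume limits are printed as "1550cGy 1000cGy" for <0.25 cc and <1.2 cc, the maximum point dose is 2000 cGy at 400 cGy per fraction, and the endpoint is myelitis of Grade 3 or higher.

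Appendix D is headed "Dose Constraints for Five Fractions". It describes its values as those of a published task group report, "reduced by 10% based on the assumption that patients on protocol have received prior systemic chemotherapy". Its Spinal Cord row gives 20.2 Gy (<0.25 cc), 12.1 Gy (<1.2 cc) and 27 Gy maximum point, again for myelitis. The low-dose spillage guidance at its end adds: "Respect all critical organ dose-volume limits listed above". It makes no exception for the cord row.

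Section 5.2 also makes the thecal sac the planning risk volume for the cord. Appendix D gives the sac a 30 Gy maximum.

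**The concern.** One structure has two sets of limits for the same volumes, endpoint and number of fractions, and the protocol gives both sets a binding role. It has no sentence on precedence. It also does not say whether the Section 5.2 table, placed after the spine paragraph, applies to a non-spine bone target close to the cord (a posterior rib lesion, for example). For such a lesion, a planner could reasonably take the cord limit from Appendix D. So could anyone who checks finished plans against the Appendix D list.

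The endpoint behind the limit is Grade 3 or higher myelitis. The trial enrolls children from just over 3 years of age and provides for more than one participating site (Section 12.6), so planning teams may read the text differently. The choice of limit decides whether a plan is acceptable or counts as a deviation. It can also affect the Section 6 judgment on whether the study dose is safe for a child under 10.

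**Working it through.** **Step 1. Check that the printed figures are not slips.** Total dose = dose per fraction × 5.

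- Section 5.2 maximum: 400 cGy × 5 = 2000 cGy = 20 Gy, as printed.
- Appendix D maximum: 5.4 × 5 = 27 Gy, as printed.
- Appendix D <0.25 cc: 4.05 × 5 = 20.25 Gy, printed 20.2.
- Appendix D <1.2 cc: 2.43 × 5 = 12.15 Gy, printed 12.1.

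The per-fraction figures agree with their totals, so the difference is neither a unit error nor rounding.

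**Step 2. Compare the two sets.**

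| Cord limit | Section 5.2 (Gy) | Appendix D (Gy) | Difference (Gy) | Appendix D / 5.2 | 5.2 / Appendix D |
|---|---|---|---|---|---|
| Maximum point | 20 | 27 | 7.0 | 1.35 | 0.74 |
| <0.25 cc | 15.5 | 20.2 | 4.7 | 1.30 | 0.77 |
| <1.2 cc | 10 | 12.1 | 2.1 | 1.21 | 0.83 |

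All three Section 5.2 values are lower, so meeting Section 5.2 means meeting Appendix D. The reverse fails: a cord maximum above 20 and up to 27 Gy passes the Appendix D point limit and breaches Section 5.2.

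**Step 3. Ask whether the 10% reduction explains the gap.** Undoing it gives 27/0.9 = 30, 20.25/0.9 = 22.5 and 12.15/0.9 = 13.5 Gy, so Section 5.2 is not the unreduced set. Applying a further 10% gives 27 × 0.9 = 24.3, 20.2 × 0.9 = 18.2 and 12.1 × 0.9 = 10.9 Gy, which are not the Section 5.2 values either. The ratios 0.74, 0.77 and 0.83 rule out any single scaling factor.

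**Step 4. Express the gap as biologically effective dose.** BED = D(1 + d/(α/β)), where D is total dose and d is dose per fraction. With α/β = 4 this reproduces Appendix B:

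- 30 Gy in 10: 30(1 + 3/4) = 52.5 Gy
- 50.4 Gy in 28: 50.4(1 + 1.8/4) = 73.08 Gy
- 54 Gy in 30: 54(1 + 1.8/4) = 78.3 Gy
- 40 Gy in 5: 40(1 + 8/4) = 120 Gy

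For the two cord maxima:

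- α/β = 4: 20(1 + 4/4) = 40.0 Gy against 27(1 + 5.4/4) = 63.45 Gy, ratio 1.59.
- α/β = 2 (an assumption for cord; the documents give no value): 20(1 + 4/2) = 60.0 Gy against 27(1 + 5.4/2) = 99.9 Gy, ratio 1.67.

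**Step 5. Thecal sac row.** The sac maximum is 30/27 = 1.11 times the Appendix D cord maximum, but 30/20 = 1.50 times the Section 5.2 maximum.

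**Step 6. What is recorded for spine targets.** Section 5.2 requires minimum, mean and maximum dose to the PTV. For spine, that is the 3000 cGy volume. The 90% coverage rule is confined to non-spine bone. If part of a spine GTV received only the PTV dose, its BED with α/β = 4 would be 30(1 + 6/4) = 75 Gy against 120 Gy, or 37.5% lower (1 − 75/120). This is an illustration only. The documents give no GTV-to-cord distances or spine lesion counts, so neither the frequency nor the extent of any shortfall can be computed.

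**The case against.** The strongest reply is that there is no true conflict. Both sets are upper limits; if both apply, the stricter one binds, and respecting Appendix D does not license exceeding Section 5.2. Section 5.2 also gives clear direction by making its own table the leading consideration straight after the spine prescription. A spine planner has to read that paragraph, because the spine doses and volumes appear nowhere else. All of this stands. A reader might infer that the protocol leaves the planner with two irreconcilable limits and no guidance. The text does not support that for spine lesions. What remains is a looser Appendix D row, no explicit precedence sentence, and silence on non-spine bone near the cord.

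A reader might also take the BED ratios as added myelitis risk, or the Appendix D row as an overdose. Neither follows. The ratios compare two ceilings, and Appendix D describes its values as published limits already lowered by 10%.

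Section 6 is a partial safeguard. It allows 3500 cGy in five fractions for children under 10 when the study dose is unsafe for normal tissue, and it requires the Principal Investigator's approval of dose modifications. It does not say which cord limit settles that question.

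On spine coverage, the PTV minimum is a lower bound on GTV dose, because the GTV lies inside the PTV. Section 10.1 also collects structures and dose in DICOM format where feasible. A shortfall could therefore often be reconstructed. The documents do not support a claim that spine lesions will be underdosed, or that their dose can never be known.

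**Conclusion.** The point holds as an internal inconsistency in a safety threshold, not as a flaw in the statistical design. The Appendix D cord limits exceed those of Section 5.2 by 35% (maximum point), 30% (<0.25 cc) and 21% (<1.2 cc), and no sentence states which set prevails. The exposure is greatest for non-spine bone near the cord and for plans checked against Appendix D alone. The dose comparison needs no outside assumption. The BED ratio of 1.59 rests on the α/β of 4 that reproduces Appendix B, and 1.67 rests on an assumed α/β of 2.

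The thecal sac row is a matter to confirm. The documents set no required ratio between the sac and cord limits, so 1.50 is not shown to be wrong. The missing spine GTV dose record is a secondary reporting gap of unknown size. Section 13.4.2 keeps all enrolled patients in the main analysis of local control, and nothing here changes the sample size, type I error or power.

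**What to change.** 1. Change the Appendix D Spinal Cord row to 20 Gy maximum point, 15.5 Gy (<0.25 cc) and 10 Gy (<1.2 cc), or replace it with a cross-reference to Section 5.2.
2. State in Section 5.2 that these limits apply to every treated site near the cord, spine or not.
3. Confirm that the thecal sac row is still intended alongside the 20 Gy cord maximum.

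This is one short amendment. Its downside is that some lesions near the cord may get slightly less target coverage than Appendix D alone would allow.

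Optional: for each spine lesion, record the GTV minimum dose and the percentage of the GTV receiving 4000 cGy. That adds two fields to the treatment form. Any numeric coverage goal is the sponsor's choice; the 90% used for non-spine bone is one candidate. It must stay subordinate to the cord limit so that it cannot raise cord dose. The all-enrolled primary analysis should stay as it is.
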